19.5 Protections Against Risks Associated with Deep Phenotyping

Quantitative Sensory Testing. Methods to reduce risks associated with QST (as conducted before and during MRI) will include the following: a) the proposed settings and methods are widely used and have been shown to be safe in extensive use worldwide; b) participants are told that they are free to stop any testing procedure at any time; c) research personnel receive extensive training and follow detailed standardized operating procedures that ensure safety, d) the maximum applied pressure intensities are set to be below levels that would cause tissue damage; e) the MAST automated pressure stimulators include redundant software, electrical, and mechanical safety features to ensure that the amount of pressure applied does not cause tissue damage, including a button that the patient or researcher can push to immediately release the device from his/her thumb; f) the maximum illuminance of the visual stimulus does not cause eye pain or eye injury; g) the lowest temperature of the cold stimulus (6°C) is not tissue damaging; h) testing is automatically stopped if participants report severe pain or discomfort (e.g., 100 on 0 to 100 scale).

MRI. Described in Section 19.4.

Back maneuvers. This procedure will be supervised by the study team, and the pain from this procedure is expected to be temporary. The frequency, duration, and type of maneuvers are entirely under patient control. Patients will decide which maneuvers to do and they will always have the option to opt out of this task or stop. Patients will be able to take their typical PRN pain medications (e.g., NSAIDs) after scanning, if they feel the

need. If participants still find the increased pain to be uncomfortable, the study team will discuss with them other self-management techniques they could use to reduce their pain. We have published with this technique before^{172,188} with few adverse events (none severe).

ANS monitoring: To minimize the risk of skin irritation, we will only use commercially available FDA-approved skin prep materials and disposable adhesive gel leads. A new set of leads will be used for each participant. Leads will not be attached to damaged, broken or irritated skin. Prior to placement and after removal skin area will be cleaned with alcohol pads. Participants will be instructed that they may stop participating at any time.

20 Potential Benefits of the Proposed Research to Research Participants and Others

Individuals assigned to any treatment arm of the study may directly benefit in terms of enhanced pain management from having access to self-management materials and non-pharmacological and pharmacological interventions. In addition, there is considerable potential benefit to future patients with chronic low back pain should this trial support the effectiveness of these alternative of opiate-based pain treatment and elucidate their underlying mechanisms. Section 13 describes the incentive payment schedule for participants.

21 Importance of Knowledge to be Gained

For patients with chronic low back pain in the United States, opioids remain a common but often counter-beneficial clinical option. Alternatives are known to be efficacious, but they are often not implemented in routine clinical care given skepticism, logistical, and resource-related barriers. In this context, the findings from this study will provide rigorous evidence regarding the effectiveness of these interventions and the underlying mechanisms. The risks in this study are reasonable in relation to the importance of knowledge to be gained in service of improved pain management.

22 Study and Participant Discontinuation

22.1 Study Discontinuation

This study may be temporarily suspended or prematurely terminated if there is sufficient reasonable cause. Written notification, documenting the reason for study suspension or termination, will be provided by the suspending or terminating party to study participants, investigator, NIAMS and regulatory authorities. If the study is prematurely terminated or suspended, the Principal Investigator (PI) will promptly inform study participants, the Institutional Review Board (IRB), and sponsor and will provide the reason(s) for the termination or suspension. Study participants will be contacted, as applicable, and be informed of changes to study visit schedule.

The interventions evaluated in this study are all tested and considered standard treatment for cLBP. Thus, there is no foreseeable possibility that any of these interventions could result in the termination of the study. A safety concern unrelated to our study is the potential spread of COVID-19 and a mandated shutdown of our study by either the university or the state of Michigan. Study may resume once concerns about safety, protocol compliance, and data quality are addressed, and satisfy the sponsor, IRB and/or Food and Drug Administration (FDA).

Circumstances that may warrant termination or suspension include, but are not limited to:

- Determination of unexpected, significant, or unacceptable risk to participants
- Demonstration of efficacy that would warrant stopping
- Insufficient compliance to protocol requirements
- Data that are not sufficiently complete and/or evaluable
- Determination that the primary endpoint has been met
- Determination of futility

22.2 Participant Discontinuation

Participants may withdraw voluntarily from the study or the PI may discontinue—a participant from the study. In some cases, a participant may withdraw from the study intervention—or be discontinued from the study intervention by the PI(s)—and still continue to participate in other aspects of the study. If the participant no longer meets the inclusion/exclusion criteria for the study, they may be withdrawn. For example, the participant becomes pregnant or is diagnosed with cancer.

If a participant chooses to withdraw from an intervention and they can still continue participation in the study. They will be asked to come in for the remaining study visits and complete the mini-assessments.

22.3 Lost to Follow-Up

A participant will be considered lost to follow-up if they fail to 3 consecutive study visits. Study staff will attempt to contact the participant 3 times after every missed visit.

23 Data Safety Monitoring Plan (DSMP)

The study team will conduct scheduled assessments of the study progress monthly for the first six months and then on a semi-annual basis. Adverse events will be reported according to FDA guidelines and will be sent to the University of Michigan IRBMED. The DSMP is described in a separate document (see DSMP).

23.1 Definitions, Collection and Reporting of Adverse Events (AEs), Serious Adverse Events (SAEs) and Unanticipated Problems (UaP)

23.1.1 Adverse Event (AE)

An AE will be defined as any unfavorable or unintended change in structure, function, signs, or symptoms temporally associated with the conduct of this study whether or not a causal relationship with the study has been established. The participants will be asked to spontaneously report any AE Date of onset and resolution (if applicable) of the AE will be documented. The PIs will monitor all AEs to the termination of subject involvement in the study or to a satisfactory resolution if the AE is ongoing.

Events will be considered study-related if classified by the PIs as definitely not, probably not, possibly, probably, or definitely related according to the definitions in *Table 7*.

Table 7: Defining Relatedness for Adverse Events

Relatedness	Definition
Definitely Not	The event is definitely not associated with study.
Probably Not	The temporal association, patient history, or clinical condition is such that the study is not likely to have had an association with the observed event.
Possibly	The event: a) follows a reasonable temporal association with the study procedures, but b) could have been produced by the patient's clinical condition or other therapy.
Probably	The event: a) follows a reasonable temporal association with the study conduct, b) abates upon discontinuation of study procedures, and c) cannot be reasonably explained by the patient's clinical condition or other therapy.
Definitely	The event: a) follows a reasonable temporal association with the study, b) abates upon discontinuation of study procedures, c) cannot be reasonably explained by the patient's clinical condition or other therapy, and d) reappears on re-exposure to the study intervention/procedures.
Unknown	Not enough information exists for the assessment of causality at the time of occurrence.

Signs and symptoms will be graded by the PIs as mild, moderate, severe, or life threatening according to the definitions below (*Table 8*).

Table 8: Defining symptom severity for adverse events and potential study risks

Score	Grade	Definition
1	Mild	Causing no limitation of usual activity
2	Moderate	Causing some limitations of usual activities
3	Severe	Causing inability to carry out usual activities
4	Life-Threatening	Patient was at immediate risk of death from the event

23.1.2 Serious Adverse Events (SAE)

A serious adverse event (SAE) is defined as any adverse event that results in one or more of the following outcomes:

- Death
- A life-threatening event
- Inpatient hospitalization or prolongation of existing hospitalization relating to study treatment
- A persistent or significant disability/incapacity hospitalization relating to study treatment
- An important medical event based upon appropriate medical judgment

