10.4 Unscheduled Non-Study Interventions Triggering Deep Assessments

It is anticipated that 10-20% of enrolled participants will get a non-study related invasive or minimally-invasive pain intervention including back surgery, epidural steroid injections or facet joint injections while enrolled in the study. To assess these common pain medicine interventions that take place outside of the study, monthly assessments will ask about plans for new treatments and also request that participants contact study staff if one of these treatments is scheduled. Participants who meet the deep phenotyping inclusion criteria will be offered an additional deep assessment visit **prior to** the medically scheduled pain intervention. Should the participant agree, then a deep phenotyping visit will be scheduled at the CPFRC to take place in advance of the intervention. Data will also be collected exploring why the patient chose to undergo this non-study intervention (e.g., not satisfied with current treatments, physician prescribed new treatment). Then, at 4 and 8 weeks after the non-study intervention participants will undergo a separate follow-up assessment (same as that used for the BACPAC consortium non-study intervention surveillance, see Section 11 below).

11 Other Unscheduled, Non-Study Interventions (NSI) Follow-Up Assessments

Other non-study interventions (NSI) are expected to occur during the course of a patient’s enrollment and will be assessed once per month for the first 6 months of study enrollment during T1-T4 and during mini-assessments as appropriate. An affirmative response regarding starting one of these NSI will trigger a short follow-up questionnaire assessment consisting of a Patient Global Assessment of Change (PGIC), pain intensity as measured by PROMIS Pain Intensity and the Low-Back Pain Specific Pain Intensity, and the PROMIS Pain Interference (4a) delivered via Qualtrics at 4 weeks and 8 weeks after the treatment. We will also assess the reasons for starting the new treatment. These follow-up assessments will only be triggered for the first NSI scheduled for a participant. Later NSIs will only be logged and inform data analysis. Treatments that will trigger these follow-up assessments are listed below:

1. Spinal fusion
2. Injections for low back pain
3. Changes to medication for low back pain

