#### 10.1.5 Study Events Reporting Requirements

A timeline for reporting AEs, SAEs, UaPs and Protocol deviations to the NIAMS Executive Secretary and the Institutional Review Board of the University of Michigan are described in Table 10.

Table 10 Timeline for Reporting Study Events to NIAMS and the IRB

Event	NIAMS Executive Secretary who will report to the DSMB and NIAMS	UM IRB
Serious Adverse Event ( Related )	Within 48 hours of the investigator becoming aware of the event	Within 7 days of occurrence notification
Serious Adverse Event (Unrelated or Anticipated)	Within 48 hours of the investigator becoming aware of the event	Annual report to IRB prior to scheduled continuing review
Non-serious adverse events grade 2 or higher ( moderate or greater )	All non-serious adverse events (even those graded as “mild”) should be reported in aggregate as part of the routine DSMP report	Annual report to IRB prior to scheduled continuing review
Any unanticipated problems that are related to the study and indicate risks to subjects	Within 48 hours of the investigator becoming aware of the event	Serious problems within 7 days of occurrence Non-serious problems within 14 days
Privacy violation or breach of confidentiality	If impacting participant safety, report within 48 hours of being notified of the occurrence; all other violations or breaches of confidentiality that do not impact participant safety can be reported as part of the routine DSMP report.	Report to IRB within 7 days Within 24 hours to the UMHS Privacy Office
Protocol deviations	If impacting participant safety, report within 48 hours of being	Annual report to IRB prior to scheduled continuing review

	notified of the occurrence; all other deviations that do not impact participant safety can be reported as part of the routine DSMP report	
--	---	--

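### Two of the five SAE criteria require relatedness to study treatment, which contradicts the 48-hour reporting row for unrelated SAEs and leaves some unrelated admissions and disabilities outside it

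*Protocol*

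**What the plan says.** Protocol 23.1.2 opens with a general rule: "A serious adverse event (SAE) is defined as any adverse event that results in one or more of the following outcomes". Five outcomes follow, and SAP 10.1.1 repeats them. Three carry no causal condition: death, a life-threatening event, and "An important medical event based upon appropriate medical judgment". The other two do:

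- "Inpatient hospitalization or prolongation of existing hospitalization relating to study treatment"
- "A persistent or significant disability/incapacity hospitalization relating to study treatment"

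The surrounding text treats causality as a separate matter. Protocol 23.1.1 and SAP 10.1 define an adverse event as a change "temporally associated with the conduct of this study whether or not a causal relationship with the study has been established". The PIs then classify relatedness on the Table 7 scale. Table 10 (Protocol 23.1.6, SAP 10.1.5) has one row for related SAEs and another whose label begins "Serious Adverse Event (Unrelated or Anticipated". Both rows require a report to the NIAMS Executive Secretary, who informs the DSMB and NIAMS, within 48 hours of the investigator's awareness. Non-serious events are pooled in the routine DSMP report. Protocol 8.2 and SAP 5.5 state that study staff are not blinded to assignment.

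**The concern.** Seriousness describes an event's outcome, and relatedness describes its cause. If relatedness is a condition of seriousness, the causal judgment decides whether the event enters the expedited system at all. The people making that judgment know the treatment assignment.

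A 48-hour row for unrelated SAEs lets someone outside the study team see the event promptly and disagree with the attribution. Protocol 23.2.1 gives the DSMB expedited review of SAE reports, unanticipated problems and safety-affecting deviations, so SAE status largely determines what it sees early. An admission filtered out by the definition does not get that second look and is missing from the SAE count.

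The protocol's own risk section shows where attribution could be hard. It names suicidality as the most serious adverse effect of duloxetine and reports worsening of psychiatric symptoms with mindfulness practice (Protocol 19.1). The trial also has no control group (SAP 5.1) against which to judge background admissions.

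**Working it through.** No arithmetic applies. The check is to set the provisions side by side and follow one event through them.

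**Relatedness in each provision**

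| Provision | Requires relatedness? |
|---|---|
| AE definition (Protocol 23.1.1, SAP 10.1) | No: "whether or not a causal relationship with the study has been established" |
| SAE: death | No |
| SAE: life-threatening event | No |
| SAE: hospitalization or its prolongation | Yes, to study treatment |
| SAE: disability or incapacity | Yes, to study treatment |
| SAE: important medical event | No, but rests on medical judgment |
| Unanticipated problem (Protocol 23.1.3, SAP 10.1.2) | Yes, to research procedures |
| Table 10, 48-hour report of SAEs | No: related and unrelated rows both exist |

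**Following an event that the PIs judge unrelated**

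1. If it is fatal, life-threatening or judged medically important, it is an SAE. It goes to the NIAMS Executive Secretary within 48 hours under the unrelated row.
2. If admission or disability is its only serious outcome and it is not judged medically important, it meets none of the five criteria. It is non-serious by definition and goes into the pooled routine report.
3. The other 48-hour route for events does not recover it. An unanticipated problem must have a reasonable possibility of having been caused by the research.

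Step 2 is the gap. Table 10 expects unrelated SAEs, but the definition stops two of the five kinds from ever being one.

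The gap is confined to the NIAMS and DSMB column of Table 10. In the IRB column, unrelated SAEs and non-serious events of grade 2 or higher both go into the annual report.

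**Three further defects in the same text**

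- The disability line runs disability and hospitalization together, so it can be read as requiring an admission as well.
- The sentence introducing Table 7 counts an event as study-related whichever of five ratings the PIs choose, including definitely not related. It therefore sets no cut-off between the two SAE rows of Table 10. Table 7 also has an Unknown rating whose handling is not stated.
- Table 7 rates relatedness to the study or its procedures, whereas the SAE condition refers to study treatment. Read literally, an admission caused by a study procedure such as MRI, sensory testing or a blood draw could also fail the hospitalization criterion.

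**The case against.** The strongest reply is that the important-medical-event criterion has no causal condition. An unrelated psychiatric admission, serious fall or unplanned operation can be classed as an SAE on medical judgment and then reported within 48 hours. A reader might infer that every admission judged unrelated escapes SAE status. The documents do not support that, because three of the five criteria remain open. This part of the reply stands and narrows the point. It does not remove it, because the safeguard is discretionary and an admission is an objective trigger.

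Table 7 also sets a low bar for a possible relation: reasonable timing is enough even if the patient's condition could explain the event. Many admissions during duloxetine treatment would probably be rated at least possibly related. That reduces how often the gap matters, although no text says that a possible rating counts as related.

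Three stronger readings on size are tempting and are not supported:

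- Protocol 10.4 says "It is anticipated that 10-20% of enrolled participants will get a non-study related invasive or minimally-invasive pain intervention". Applied to the 500 to 600 recruits in Protocol section 8, this gives 10% × 500 = 50 to 20% × 600 = 120 people. These are people having procedures, including epidural and facet joint injections. They are not admissions, and no inpatient share is given.
- A delay of six months might be read from the study team's semi-annual assessments (Protocol section 23) or the DSMB's at-least-semiannual meetings (23.2.1). The interval of the routine DSMP report is not stated.
- The filter might act more on some arms than on others. Nothing in the documents shows this.

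It is also true that these events are still recorded as adverse events. The safety alarm in Protocol 18.1.5 and SAP section 10 counts related events of grade 2 or higher and does not use SAE status, so its thresholds are untouched. The DSMP is a separate document that was not available for this review and may define SAEs differently.

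**Conclusion.** The definition is wrong as written and should be corrected. It makes seriousness depend on causality for two of five criteria, in both documents, and contradicts the AE definition, Table 7 and Table 10.

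The consequence is specific. An event drops from a 48-hour report to the pooled routine report when all three of these hold: its only serious outcome is hospitalization or disability, the unblinded PIs judge it unrelated, and it is not judged medically important. Neither the number of such events nor the length of the delay can be derived from the documents. No endpoint, power figure or alarm threshold changes.

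The conclusion assumes that staff apply the definition literally and that the DSMP does not override it. If the DSMP does differ, it is a further text to reconcile.

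**What to change.** - In Protocol 23.1.2 and SAP 10.1.1, delete the closing condition about study treatment from the hospitalization and disability criteria.
- In the disability line, also remove the stray word hospitalization, so that persistent or significant disability or incapacity stands alone.
- Leave causality to Table 7 and the two SAE rows of Table 10.
- In Protocol 23.1.1 and SAP 10.1, rewrite the sentence before Table 7 so that it states which ratings count as related and which as unrelated, and say how Unknown is handled. The safety alarm also counts related events, so it benefits from the same cut-off.
- Check the DSMP for the same wording and align it.

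The cost is a few words in each document and some additional 48-hour reports of admissions that prove unrelated, which Table 10 already provides for. No treatment, visit or analysis changes.

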23.1.3 Unanticipated Problem (UaP) Definition

An unanticipated problem may be either an actual harmful or unfavorable occurrence or any development that potentially increased the likelihood of harm occurring in the future. Assessment Criteria:

- **Unanticipated Severity:** The nature, severity, or frequency of the event(s) or information was NOT expected, given descriptions in the study documents or the characteristics of the subject population being studied.
- **Related:** There is a reasonable possibility that the procedures involved in the research caused the problem.
- **Increased Risk:** The event(s) or information suggests that the research places subjects or others at a greater risk of harm than was previously known or recognized (including physical, psychological, economic, or social harm).

23.1.4 Protocol Deviation (PD)

An accidental or unintentional change to, or non-compliance with the research protocol that does not increase risk or decrease benefit or; does not have a significant effect on the subject's rights, safety or welfare; and/or on the integrity of the data. Deviations may result from the action of the subject, researcher, or research staff. Departure from the IRB approved research protocol without prior IRB approval for the variation.

23.1.5 Expected Adverse Events

The following table describes expected adverse events in for this study (*Table 9*). Participant safety monitoring and the process of halting the study is further described in Section 22.

Table 9: Management of expected study adverse events

Expected Adverse Event	Criteria for Management	Intervention Modification, if any
Biospecimen Collection		
Bruising/Hematoma at site of draw	Participant may verbally report this.	Participant can apply ice to the area.
Discomfort with Physical Therapy		
Muscle soreness Back Pain Fatigue Bruising Psychological distress	Participant reports symptoms lasting more than 2 hours. Participant verbalizes this.	Participants can stop as needed. Modification may be made to the PT program. Modification to be determined by Physical Therapist.
Mindfulness-based Stress Reduction (MBSR)		
Feelings of de-realization, exacerbation of psychiatric symptoms or clinical deterioration.	Clinical worsening of depression and other psychiatric symptom.	Will be evaluated by clinical psychologist on the study team who may refer the participant for appropriate treatment including emergency service if required.
Muscle soreness or injury	Participant verbalizes.	All reports of higher symptoms will be discussed to determine if modifications to the program need to be made.
Acupressure		
Mild bruising at acupressure sites	Participant verbalizes bruising.	The participant is free to withdraw from the intervention if the self-acupressure intervention becomes uncomfortable.
Duloxetine		
Nausea, vomiting, dry mouth, constipation, diarrhea, fatigue, and difficulty sleeping.	Participant verbalizes experiencing.	Study doctors will evaluate the participant. Participants have the option to stay on lower dose or stopping the medications.
Thoughts of self-harm or suicidal ideation		Participants may be referred for appropriate treatment including emergency services if required. Participation can also be discontinued if there is active suicidal ideation.
Quantitative Sensory Testing		
Residual Soreness at testing site Headache, nausea	Participants displaying sustained pain over 48 hours post testing.	Participants will be allowed to take NSAIDs. Stimuli duration and timing may be reduced. Follow up visual stimulation may be omitted or reduced at the follow up visit.

	Participant verbalizes residual headache, or nausea.	
Autonomic Nervous System Monitoring (BIOPAC)		
Irritation to the skin	Participant verbalizes	Participants will be instructed they can stop participating at any time. Follow up autonomic nervous system monitoring may be omitted.
Anxiety or general unease	Participant verbalizes	
MRI		
Claustrophobic		Participants may stop the session at any time.
Discomfort from noise		The follow up visit may omit the MRI session.
Pheno Device		
Slight low back muscle fatigue or soreness the following day similar to a light workout	Participant verbalizes	Participants will be instructed to move as fast and as far as they can COMFORTABLY and can stop at any time. Researchers will be trained on all study procedures to protect participants.
Exacerbation of pain symptoms or condition following the motion assessment if the participant is a back pain patient	Participant verbalizes	Patient participants will conduct research visits in a clinical environment under close supervision.
Participant loses balance when performing motion test and falls		
Cross contamination of infectious element between patients		The device will be cleaned thoroughly using hospital-grade sanitizing wipes after each use. Participants will wear the motion sensor harness over their clothing to avoid contact with skin.
Breach of Confidentiality		The software has undergone a risk assessment by UMHS IT and has been approved to store PHI.
Allergic reaction to harness materials		Participant-touching materials do not contain latex and use fabrics and materials that are standard in clothing.

Electrical leakage from IMU sensors resulting in shock		
Motion sensors are an off the shelf product that have been made for wearable human use. Motion sensors are battery powered, encased in plastic, and are low voltage devices. The harnesses are constructed of electrically insulating materials, providing an additional layer of protection. The charger system has a product safety mark.
 
Device will be evaluated by UMMHS Clinical Engineering to be within the prescribed tolerance for patient contact.

Participant piercings or other wearable materials (e.g. insulin pump) snag during motion testing		
Software will include instructions and researcher user training to instruct participants to remove or secure all wearables that could snag during motion prior to testing.

Sensors interfere with performance of other devices, including medical devices		
Sensors are tested to Federal Communications Commission for Bluetooth Transmission standards and the IMU sensors' Bluetooth signal is similar to that of a wireless mouse or headphones.
 
Device will be evaluated by UMHS Clinical Engineering to be within the prescribed tolerance for patient contact.

